#### 4.4 The subjects withdrew from the test standard

( 1 ) It is necessary for researchers to stop the trial from the perspective of medical ethics ;

( 2 ) patients with severe adverse reactions ( SAE ), complications or special physiological changes should not continue to accept the test ;

( 3 ) Pregnancy during treatment.

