### 7.2 Visit 1 (D28±3d)

- ( 1 ) Evaluation of HAMD-24 scale ;
- ( 2 ) PSQI scale assessment ;
- ( 3 ) Record drug combination and adverse events ;
- ( 4 ) Drug recovery and distribution.

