### 7.3 Visit 2 (D90±3d)

- ( 1 ) Evaluation of HAMD-24 scale ;
- ( 2 ) PSQI scale assessment ;
- ( 3 ) Fecal specimen collection ;
- ( 4 ) Thyroid function test residual blood collection ;
- ( 5 ) Record the combined medication and adverse events ;
- ( 6 ) Drug recovery.

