#### ( 3 ) Immune enhancement

## **IX.Evaluation of adverse events**

1.Definition of adverse events : Any disease that occurs during a drug clinical trial, new symptoms, signs or abnormal laboratory tests, or deterioration of the original symptoms and signs, whether or not related to the test drug, is an adverse event.

---

2. Relationship between adverse reactions and experimental drugs : Searching through the CNKI database, no side effects and related adverse reactions of Ganoderma lucidum were found in the current study. If complained of discomfort, through laboratory tests such as blood routine, liver and kidney function, platelets, hemoglobin, determine or determine whether it is related to the test drug.

3. Adverse event recording and reporting channels :

In the event of adverse events, the occurrence time, clinical manifestations, treatment process and duration, outcome and the relationship between the test drugs should be recorded in detail on the case report form page. Serious adverse events should fill in the serious adverse events form and report to SFDA Registry Drug Research and Supervision Office within 24 hours, notify the team leader unit and the bidder, and report to the center ethics committee, and submit details within 7 days thereafter.

Safety evaluation at the end of the trial should include all patients who have used the test drug, regardless of whether they meet the evaluable criteria.

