### **2. statistical analysis plan**

---

Statistical analysis was performed using SPSS 9.1.3 statistical software.

( 1 ) Distribution of two groups of cases : the comparison of the shedding and elimination rates of the two groups was performed by  $\chi^2$  test or exact probability method.

( 2 ) Comparability analysis : Demographic data and other basic indicators were compared to measure the comparability of the two groups. According to the type and distribution of data,  $\chi^2$  test or exact probability method, CMH test, t test, variance analysis or non-parametric statistical method were used.

( 3 ) Compliance analysis : To compare whether the two groups of patients use the test drugs on time and in quantity. The drugs that were not banned in the regimen were mainly tested by  $\chi^2$  test or exact probability method.

( 4 ) Validity analysis : Repeated measures were used to compare the differences in measurement data such as depression scores and sleep scores between the experimental group and the control group, or linear regression models were used to control baseline depression scores or sleep scores. Differences in depression scores and sleep scores between the two groups. Compare the score after the end of the experiment with the baseline score, calculate the difference before and after the change, and use the t test to compare the difference between the score changes of the experimental group and the control group.

( 5 ) Safety analysis : adverse reactions were statistically described, and the incidence of adverse reactions in the two groups was compared by  $\chi^2$  test or exact probability method.

( 6 ) All statistical tests should give test statistics and corresponding p values. When using the exact probability method, the p value is given directly.  $P \leq 0.05$  indicated that the difference was statistically significant.

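### The only planned between-arm safety comparison is of 'adverse reactions', an undefined term that read literally covers only events judged drug-related; no comparison of all adverse events or of serious adverse events is specified.

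*Combined protocol and SAP*

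**What the plan says.** **What is collected.** Section IX.1 defines an adverse event broadly: any new or worsening condition during the trial, "whether or not related to the test drug, is an adverse event". Section 7.2 (Visit 1, day 28) lists "Record drug combination and adverse events" and section 7.3 (Visit 2, day 90) lists "Record the combined medication and adverse events". Section IX.3 asks for the timing, presentation, treatment and duration of each event, and adds that its "outcome and the relationship between the test drugs should be recorded in detail on the case report form page". Every event should therefore be on the case report form together with a causality assessment.

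**Who is analysed.** Section X.1(3) builds the safety analysis set (SAS) from randomised patients with at least one dose and a safety evaluation. The last paragraph of IX.3 asks that the end-of-trial safety evaluation include all treated patients. Both define the patients; neither says which events are counted.

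**What is compared.** Section X.2(5) is the only statement on safety statistics: "adverse reactions were statistically described, and the incidence of adverse reactions in the two groups was compared", by chi-square or exact test. The plan names no description or test of all adverse events or of serious adverse events.

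**The concern.** Between collection and analysis the wording moves from adverse events to adverse reactions. In common usage an adverse reaction is an event attributed to the drug. On that meaning, the only arm comparison for safety counts an event only if someone has judged it related.

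A randomised, placebo-controlled comparison of all events needs no such judgement, because background events are expected at the same rate in both arms and any excess shows in the difference. Filtering on causality makes the result depend on how accurate individual attributions are. If attribution is poor, a real excess in the recorded data could go undetected in the one test that the plan specifies. If the term was meant more broadly, the numerator of that test is not fixed in advance and could be settled after the data are seen.

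**Working it through.** **Step 1: how the protocol uses the term.** No definition of adverse reaction appears. The uses that bear on its meaning are these:

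- Section IX.1 and IX.3 use adverse event for definition, recording and reporting, independent of causality.
- Section IX.2 is headed "Relationship between adverse reactions and experimental drugs" and goes on to how relatedness is to be determined. If a reaction were related by definition, nothing would be left to determine.
- Section 4.4(2) refers to "patients with severe adverse reactions ( SAE ), complications or special physiological changes", attaching the abbreviation for serious adverse events to reactions.
- Section XI.3 (emergency unblinding) speaks of serious adverse reactions with no causality condition.
- Section X.2(5) uses adverse reactions alone, with no cross-reference to IX.1.

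The literal reading of X.2(5) is the drug-related subset. The looser reading, all adverse events, is also open. The text does not decide between them.

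**Step 2: what the literal reading could cost.** The plan states no adverse-event rate, so there is no figure of its own to reproduce.

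*Inputs from the plan:* 200 experimental and 100 control patients (section 5.1) and significance at P ≤ 0.05 (section X.2(6)). Sidedness is not stated, so two-sided is assumed.

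*Other assumptions:* all-event incidence of 25% versus 10%, or 20% versus 10%; the share *b* of background events judged related; the share *e* of excess (drug-caused) events judged related; and no loss of patients from the safety set.

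*Formulas.* With control rate p_C and experimental rate p_E:

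- related rate, control = b × p_C
- related rate, experimental = b × p_C + e × (p_E − p_C)

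Power is the exact probability, summed over all outcomes of Binomial(200) and Binomial(100), that the pooled two-proportion test (equivalent to the uncorrected chi-square test) has |z| ≥ 1.96.

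*Worked example,* 25% versus 10% with b = 30% and e = 70%: control 0.30 × 10% = 3.0%; experimental 3.0% + 0.70 × 15% = 13.5%.

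| Events counted | Rates from 25% v 10% | Power | Rates from 20% v 10% | Power |
|---|---|---|---|---|
| All events | 25% v 10% | 0.902 | 20% v 10% | 0.613 |
| Related, b = e = 50% | 12.5% v 5% | 0.544 | 10% v 5% | 0.291 |
| Related, b = e = 30% | 7.5% v 3% | 0.314 | 6% v 3% | 0.166 |
| Related, b = 40%, e = 60% | 13% v 4% | 0.736 | 10% v 4% | 0.433 |
| Related, b = 30%, e = 70% | 13.5% v 3% | 0.887 | 10% v 3% | 0.605 |
| Related, b = 20%, e = 80% | 14% v 2% | 0.970 | 10% v 2% | 0.785 |

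**Step 3: reading the table.** When attribution is no better than random (b = e), restriction cuts power sharply. When it discriminates well, little is lost, and at b = 20% and e = 80% power exceeds that for all events. The documents give no basis for choosing a row.

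**The case against.** The strongest reply is that X.2(5) is loosely worded or loosely translated and means all adverse events. The uses in 4.4(2), the heading of IX.2 and XI.3 support this. It stands to this extent: a reader might infer that unrelated events will certainly be left out of the comparison, and the documents do not establish that. It does not remove the point, because an undefined term still leaves the content of the only safety test open, and the same edit resolves either reading.

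A second reply is that nothing is lost: all events are on the case report form, the SAS carries no causality filter, and nothing forbids an all-event table. That is also true. The gap is that no such table or test is planned.

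A reader might further infer that the protocol steers investigators towards calling events unrelated, since IX.2 reports from a literature search that "no side effects and related adverse reactions of Ganoderma lucidum were found in the current study". The documents do not support this. IX.2 then prescribes laboratory work-up to decide relatedness case by case and contains no presumption of unrelatedness. The design is double-blind (section III), so under intact blinding a general leaning would act on both arms; it could reduce power but would not favour one arm.

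Finally, quoting only the equal-share rows would present restriction as always costly. The other rows show that it need not be.

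**Conclusion.** The point holds as a gap in specification. X.2(5) limits the only between-arm safety test to an undefined category whose literal meaning is events judged drug-related, and no comparison of all adverse events or of serious adverse events is specified, although the data for both are to be collected.

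Neither the size nor the direction of the effect on power can be determined from the documents. For assumed all-event rates of 25% versus 10%, power is 0.90 with all events and about 0.31 to 0.97 with related events only. For 20% versus 10% it is 0.61 against about 0.17 to 0.785. These figures rest on assumed incidences, assumed attribution shares, a two-sided 5% test and full safety-set numbers. They show how far the result would depend on attribution; they do not predict a loss. Efficacy analyses and sample size are unaffected.

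**What to change.** Rewrite X.2(5) along these lines: *The incidence of all adverse events, and of serious adverse events, will be described and compared between arms in the SAS by chi-square or exact test. Events judged drug-related will be presented in a secondary table.*

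Add a one-line definition of adverse reaction beside the definition in IX.1, and use the two terms consistently in 4.4, IX, X.2 and XI.3.

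The cost is one rewritten sentence, a definition, and one or two extra tables. The events and their causality assessments are already required on the case report form, so no new data, visits or patients are needed.

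### The only planned safety comparison, X.2(5), names adverse reactions; it should state that it covers all adverse events as IX.1 defines them, with drug-related ones as a subset

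*Combined protocol and SAP*

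**What the plan says.** The plan has one safety analysis, item (5) under the statistical analysis plan in section X: "adverse reactions were statistically described, and the incidence of adverse reactions in the two groups was compared", by chi-square or exact test.

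Section IX.1 sets a wider definition. It covers any illness, new symptom or sign, or abnormal test during the trial, "or deterioration of the original symptoms and signs, whether or not related to the test drug, is an adverse event".

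Collection follows that definition. At D28 the visit list reads "Record drug combination and adverse events", and at D90 "Record the combined medication and adverse events". HAMD-24 is scored at both visits.

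Relatedness is a separate field: IX.3 asks that "outcome and the relationship between the test drugs should be recorded in detail on the case report form page". For a patient who complains of discomfort, IX.2 says how it is judged: "through laboratory tests such as blood routine, liver and kidney function, platelets, hemoglobin, determine or determine whether it is related to the test drug". IX.3 ends with a coverage rule: "Safety evaluation at the end of the trial should include all patients who have used the test drug".

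**The concern.** The trial collects events of any cause, but the sentence that says what will be compared uses the narrower term. Because relatedness is on the case report form, someone following X.2(5) to the letter could filter on it and leave unrelated events out of the by-arm comparison.

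Worsening depression is the case that matters most. Patients enter at HAMD-24 8-20 (4.1) and may not take antidepressants during the trial (VI). Worsening is therefore a foreseeable harm, and IX.1 counts it as an adverse event whatever its cause. The tests named in IX.2 do not measure mood, so they give little basis for calling a worsening of depression drug-related. A comparison limited to reactions could leave it out.

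**Working it through.** **1. The texts side by side.**

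| Place | Subject | Limited to drug-related? |
|---|---|---|
| IX.1 | Definition of an adverse event | No, expressly not |
| 7.2, 7.3 | What is recorded at D28 and D90 | No |
| IX.3, recording | Relatedness noted for each event | No, but it makes a filter possible |
| IX.3, last sentence | Which patients enter the safety evaluation | Silent on event type |
| X.1(3) | Safety set: randomised, at least one dose, a safety evaluation | Silent on event type |
| X.2(5) | What is described and compared by arm | Literally, yes |

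No sentence says that X.2(5) covers all IX.1 events. Other items in X.2 do not fill the gap: (1) compares shedding and elimination rates, and (4) compares scores and changes in score.

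**2. Size of the literal reading.** The plan gives no adverse-event rate, so there is no figure of its own to reproduce. If a share r of all events is judged related, a literal X.2(5) shows r of them and omits 1 - r. The documents do not give r, so the omitted share can lie anywhere from 0 to 1.

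**3. Precision of a by-arm comparison.** Section 5.1 gives 200 v 100 patients and 15% assumed shedding, which leaves 200 x 0.85 = 170 and 100 x 0.85 = 85. The event rates below are assumptions. The Newcombe 95% interval for active minus placebo combines the Wilson limits (l, u) of each arm: lower = d - sqrt[(p1 - l1)² + (u2 - p2)²], upper = d + sqrt[(u1 - p1)² + (p2 - l2)²].

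For 10/200 v 5/100, d = 0 and the Wilson limits are 2.74-8.96% and 2.15-11.18%.
- Lower: -sqrt(2.26² + 6.18²) = -6.6 points.
- Upper: sqrt(3.96² + 2.85²) = +4.9 points.

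| Active v placebo | 95% interval, percentage points |
|---|---|
| 0/200 v 0/100 | -3.7 to +1.9 |
| 4/200 v 2/100 | -5.1 to +3.4 |
| 10/200 v 5/100 | -6.6 to +4.9 |
| 20/200 v 10/100 | -8.2 to +6.7 |
| 8/170 v 4/85 | -7.2 to +5.2 |

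Fisher exact power (two-sided, P ≤ 0.05, 200 v 100) is 27% for 10% active v 5% placebo, and 16% for 5% v 2%. For uncommon events, intervals tell the reader more than P values.

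**4. Would a HAMD-24 band count capture worsening?** Section 8.1(1) defines bands 21-35 and 36-76, and section X uses neither. The plan gives no HAMD-24 mean, SD or correlation, so this step is assumption only. Normal scores were used with mean/SD 10/5, 13/5 or 14/6, rounded and limited to 8-20 at entry. The baseline-to-D90 correlation was 0.6 or 0.8, with an average shift of 0, -2 or -4 points on top of regression to the mean.

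| Quantity at D90 | Shift 0 | Shift -2 | Shift -4 |
|---|---|---|---|
| Patients of 300 scoring 21 or more | 5-32 | 1-16 | 0-7 |
| Crossers who rose by 2 points or less | 10-25% | 13-37% | 17-49% |
| Patients rising 5 or more points who stay below 21 | 59-88% | 66-91% | 72-94% |

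The 5-point rise is an illustration; the documents set no threshold. The count misses most larger rises and includes some very small ones.

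**The case against.** The strongest reply is that nothing narrower was meant. Section 4.4 glosses SAE as severe adverse reactions, and XI.3 uses serious adverse reactions as a trigger for unblinding. IX.2 speaks of adverse reactions and then sets out to decide whether they are related, which would be circular if the word already meant related. X.2(5) names no filter, and the plan sets no relatedness categories or cut-off. This stands as a reason to rate the point low. It does not remove it, because no sentence says that X.2(5) covers all events, and the closing rule of IX.3 fixes the patients, not the event types.

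Existing safeguards also count. Patients with severe symptoms who need antidepressants are excluded (4.2), withdrawal is allowed on ethical grounds (4.4), and emergency unblinding covers deterioration (XI.3). Unblinded cases become shedding cases, whose rate X.2(1) compares by arm, though not by reason.

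Two stronger readings are tempting. A reader might infer that the plan hides harm. It does not show this: events of any cause and HAMD-24 are both recorded at D28 and D90, and the doubt concerns only what is reported. A reader might also infer that a band table is needed because it would give the number whose depression worsened. It would not, as step 4 shows. Nor could a listing of patients withdrawn or unblinded for worsening be promised from existing data, because no section clearly requires that reason to be captured.

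**Conclusion.** The point holds as a low-severity matter of wording and reporting. X.2(5) should say which events it covers, because its literal wording is narrower than IX.1 and than what the visits collect. The size cannot be fixed from the documents: the literal reading could omit anywhere from none to all of the recorded events, and omits nothing if reactions was simply meant as events. That conclusion rests on the text alone and does not depend on the simulation.

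The HAMD-24 band count is optional. Sample size, significance level and every efficacy analysis stay as they are.

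**What to change.** Reword X.2(5) to describe and compare by arm, in the safety set, all adverse events as defined in IX.1, with events judged drug-related shown as a subset. Give the arm difference with a 95% interval beside the planned test. The cost is one further row or table from data already collected.

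Optionally, add a descriptive by-arm count, without a test, of observed HAMD-24 scores of 21 or more at D28 and at D90. Use no carried-forward values, and give as denominator the treated patients scored at that visit. Label it as a count of band crossings and not of all worsening. Its drawbacks are small counts, wide intervals and some crossings of one or two points.

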## **II.test purpose**

1. In this study, the antidepressant mechanism of ganoderma lucidum spore powder was studied by microbial 16 s diversity analysis and metabolomics method, and the clinical efficacy of ganoderma lucidum spore powder intervention on postoperative depressive symptoms of papillary thyroid carcinoma was determined.
2. To investigate the effect of Ganoderma lucidum spore powder on the depression of patients through the communication pathway of microbial-intestinal-brain axis ( biosynthesis and metabolic pathway of tryptophan ), or through other microbial metabolites ( amino acids, fatty acids, short-chain fatty acids, etc. ) to inhibit the occurrence of depression in patients. To clarify the antidepressant mechanism of

---

wall-removed Ganoderma lucidum spore powder and provide objective basis for its application.

[figure not shown]
3. To construct a clinical database of patients with depressive symptoms after papillary thyroid carcinoma surgery, and to explore the optimal mode of intervention of exfoliated ganoderma lucidum spore powder in patients with depressive symptoms.

The multi-omics platforms such as metabolomics and intestinal flora were used to directly find the functional components related to the intervention effect of wall-removed Ganoderma lucidum spore powder ; combined with clinical data, mining potential clinical indicators or more sensitive biomarkers ; on this basis, the in vivo function and mechanism of the target flora ( potential metabolic beneficial bacteria ) or metabolites ( potential epigenetic or parabiotic ) alone or in combination will be verified.

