### 8.2 secondary index

#### ( 1 ) Changes of intestinal microbial diversity and metabolites in patients

( 2 ) Remission of sleep status : After 90 days of treatment, the Pittsburgh Sleep Quality Index score decreased.

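### Section X sets one P ≤ 0.05 rule with no multiplicity control, which is unsafe if it is applied feature by feature in the planned 16S and metabolomics screen

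*Combined protocol and SAP*

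**What the plan says.** Section 8.2(1) lists "Changes of intestinal microbial diversity and metabolites in patients" as a secondary index. Section II, purpose 2, names candidate routes: "biosynthesis and metabolic pathway of tryptophan", and other microbial metabolites (amino acids, fatty acids, short-chain fatty acids, with an open-ended "and so on" in effect). Purpose 3 goes further. Multi-omics platforms are to "directly find the functional components related to the intervention effect", and clinical data are combined with them for "mining potential clinical indicators or more sensitive biomarkers". Laboratory verification follows from what is found: "on this basis, the in vivo function and mechanism of the target flora" and of metabolites.

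Stool and residual blood are taken at week 0 (Section 7.1) and D90 (Section 7.3), and at no other visit. Section 7.4 covers collection, storage and transport of specimens only.

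In Section X.2, item (4) gives repeated measures, baseline-adjusted linear regression and a t test on change for "measurement data such as depression scores and sleep scores between the experimental group and the control group". Item (6) begins "All statistical tests should give test statistics and corresponding p values" and ends with the single criterion, that P ≤ 0.05 "indicated that the difference was statistically significant". Section X.1 fills missing data in the full analysis set by LOCF. No diversity index, feature-level model, feature filter, selection rule, or FDR or family-wise control appears.

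**The concern.** A 16S or metabolomics screen can test many features at once. A per-test 5% threshold then returns some hits even if the powder does nothing, so a list with entries on it is weak evidence of mechanism. Purpose 3 takes the selected flora or metabolites into further work, so errors at selection are carried forward. With no rule written down, the choice of features, model and threshold stays open until the group codes have been given to the analysts, and a reader could not tell planned results from post hoc ones.

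**Working it through.** **The plan's own figure.** Section 5.1 inflates 100 pairs for 15% shedding. 100 / 0.85 = 117.65, against 117 stated, so it agrees to rounding. There is no stated feature count, omics effect size or omics power to reproduce.

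**Inputs from the plan.** Per-test threshold 0.05 (X.2(6)); 200 versus 100 patients and 15% shedding (Section 5.1).

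**Inputs assumed.** Number of features m; share responding; effect size; correlation between features; two-sided tests; shedding applying equally to specimens, which gives 200 × 0.85 = 170 and 100 × 0.85 = 85 evaluable.

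**1. False hits when nothing responds.** The expected number is 0.05 × m, whatever the correlation: 0.1, 1, 5 and 15 for m = 2, 20, 100 and 300. The chance of at least one is 1 − 0.95^m if features are independent. At a common correlation of 0.6 it was simulated.

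| m | Expected false hits | P(at least one), independent | P(at least one), correlation 0.6 |
|---|---|---|---|
| 20 | 1 | 64% | 37% |
| 100 | 5 | 99% | 65% |
| 300 | 15 | about 100% | 84% |

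**2. Expected composition of the hit list when some features respond.** Take m = 300 with 5% responding (15 features) at 0.3 SD. Two-sided t-test power at 85 versus 170 is 0.614.
- Expected false hits: 285 × 0.05 = 14.25.
- Expected true hits: 15 × 0.614 = 9.21.
- Ratio of expected counts: 14.25 / (14.25 + 9.21) = 61%.
- At 0.5 SD, power is 0.963 and the ratio is 14.25 / (14.25 + 14.45) = 50%.
- If 20% respond, the ratios are 0.04 / (0.04 + 0.2 × 0.614) = 25% and 0.04 / (0.04 + 0.2 × 0.963) = 17%.

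**3. What a single trial would show.** The ratio above uses averages and hides the effect of correlation. The same design (300 features, 15 responding at 0.3 SD, 85 versus 170) was simulated with normal test statistics. The responding features were shifted by 0.3 / √(1/85 + 1/170) = 2.26 standard errors.

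| Common correlation | Mean per-trial false share | Median false hits |
|---|---|---|
| 0 | about 60% | 14 |
| 0.3 | 53% | 10 |
| 0.6 | 37% | 3 |

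The mean number of false hits stays near 14 throughout. With strong correlation it comes from a minority of trials with very many false hits, while the typical trial has few.

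**4. LOCF.** Specimens exist only at week 0 and D90. If Section X.1 were applied to omics data, a missing D90 value would be replaced by the week-0 value, so that patient would be recorded as unchanged.

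**The case against.** *P ≤ 0.05 may not be the selection rule.* A reader might infer that the plan commits to picking features by unadjusted P ≤ 0.05 alone. The documents do not say that. Purpose 3 combines omics with clinical data and states no rule for choosing features. What stands is that no other criterion is written, and item (6) follows on from a sentence covering all tests.

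*A method is arguably given.* The wording of X.2(4) is open enough to include omics values as measurement data. That is a fair reading, so it would be too strong to say the plan offers no usable method. It brings in generic models only, with no error control.

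*The declared index may be narrow.* Section 8.2(1) speaks of microbial diversity, which can mean a few indices, and the documents do not say whether metabolomics is targeted or untargeted. This objection stands and limits the point: the many-feature problem arises from the screen in purpose 3.

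*The size is assumed.* It is also tempting to say that most hits in this trial would be false. That depends on feature count, response share, effect and correlation, none of which is in the documents. At correlation 0.6 the mean share is 37%, and if 20% respond at 0.3 SD the ratio of expected counts is 25%.

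*Outputs are called potential and will be verified.* True, and this softens the consequence. Verification comes after selection, however, and does not control what is selected.

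**Conclusion.** The gap is real but conditional. Section X gives one P ≤ 0.05 rule and no multiplicity control, while a secondary index and a stated purpose rest on omics data. If the rule is applied feature by feature, about one null feature in twenty passes on average. In the illustrated 300-feature screen at 0.3 SD, between roughly 37% and 60% of a trial's hits are false on average, depending on correlation. Only the threshold, the 2:1 allocation and the 15% shedding come from the plan; the other inputs are assumptions.

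The change should be made if many features are screened. It matters much less if only a few diversity indices or pre-named metabolites are tested. Nothing here affects the HAMD leading indicator, and it does not follow that the mechanism findings would be wrong, only that an unadjusted list would be weak support for them.

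**What to change.** Before unblinding, add an omics item to X.2:

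- **(a) Comparison.** Compare each 16S and metabolomic feature between arms at D90, adjusted for its baseline value, in patients with both specimens. Do not apply LOCF to omics data.
- **(b) Error control.** For feature-level results, replace unadjusted P ≤ 0.05 with Benjamini-Hochberg FDR control within each defined family (16S; each metabolomics specimen type). Fix q in advance with a reason, and report q-values. Fix the features tested in each family by a prevalence or detection filter that is blind to arm.
- **(c) Named family.** Define one separate FDR-controlled family: diversity indices chosen by the sponsor before unblinding (Section II names none), plus the metabolite classes in purpose 2 (tryptophan pathway, amino acids, fatty acids, short-chain fatty acids). Exclude its members from the broad families.
- **(d) Labelling.** Call all other features exploratory, even if they pass the FDR threshold.

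The cost is a short text addition, no new samples or visits, and fewer hits. In the 300-feature design at 0.3 SD, unadjusted testing finds about 9 of the 15 responding features. Under FDR control:

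| | q = 0.05 | q = 0.10 | q = 0.20 |
|---|---|---|---|
| Mean true hits, independent | 1.5 | 2.4 | 3.9 |
| Mean true hits, correlation 0.6 | 2.0 | 2.9 | 4.1 |
| Mean false share, independent | 5% | 9–10% | 19% |
| Trials keeping no true hit, independent | 32–34% | 18–20% | 7–8% |
| Same, correlation 0.3 | 51% | 40% | 27% |
| Same, correlation 0.6 | 66% | 58% | 47% |

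At 0.5 SD the share of trials keeping no true hit is near 0% if features are independent and about 8% / 4% / 1% at correlation 0.6. The loss is therefore substantial for small effects in correlated data. That is why q needs a stated reason; a lenient value may suit a screen that will be followed by verification.
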